11.0 Specimen Collection and Banking

No specimens will be collected.

12.0 Data Management

The MUSC CCCR Patient Resource Core (Pro00021985) will act as an honest broker for the provision of clinical data of patients that fit criteria and are already enrolled in the CCCR study. The clinical data provided to the PN and PI of this study will include all data listed in sections 4.0 & 10.0 and will be provided to study staff de-identified. The data provided will only include 25 patient data sets for the "Usual Care" group that has not had contact with the patient navigator and serves as the control group for this study.

Analyses will be primarily descriptive in nature. Means, standard deviations, medians, inter-quartile ranges, and proportions will be reported on each outcome of interest, as appropriate. These statistics will be reported at baseline, 3 months, 6 months, and at 12 months for the primary outcome measure (Medication Adherence) and all secondary outcome measures. The secondary outcome measures are 1) Adherence with Primary Care and Specialty Care Visits, 2) Adherence with Lab and other Study Appointments, 3) Healthcare Utilization, 4) Disease-related Damage, 5) Corticosteroid Use and 6) Patient-Reported Outcomes.

In addition to results reported by our site, we will report results from our collaborating site, University of Alabama at Birmingham (UAB), during their implementation of the LPNP protocol.

Analyses will include estimates of site to site variability utilizing a combined MUSC and UAB dataset. All data sharing will be de-identified and maintained on MUSC's supported REDCap platform. Shared data and analyses were included in the Scope of Work executed by NIH subaward funding of 3P30AR072582-03S1, Improving Minority Health in Rheumatic Diseases.

Although this is not a randomized trial, we will use statistical methods such as propensity score weighting (36) to gain an understanding of how the use of PNs improves outcomes (e.g. medication adherence) when compared to usual care. Generalized linear mixed models will be used in conjunction with propensity score weighting to compare treatment group outcomes and estimate relevant effect sizes while adjusting for relevant baseline covariates (e.g. age, SLEDAI) and accounting for repeated measures within patients over time.

Since we will have all healthcare utilization data over the 12-month time, calculations will also be performed to indicate how intervention and control patients compared monthly throughout the study. These data will help us design a larger randomized, multi-center, clinical trial. The pilot study will be extremely valuable both in demonstrating feasibility and in providing data for sample size estimation for our next step trial.

Since this is a pilot study, our sample size of n=25 patients in the PN group and n=25 patients in the "Usual Care" group were selected primarily to ensure that we can assess feasibility of providing this intervention in this high-risk population. Having n=25 patients in each group will also allow us to estimate group-specific outcomes with relatively strong precision (i.e. within \pm 0.3 standard deviations for continuous outcomes and \pm 10%-20% percentage points for proportions). All this information will be vital for designing a future, definitive randomized controlled trial. In obtaining preliminary estimates of effectiveness, our sample sizes will also provide sufficient power (>80%) to detect moderate differences in medication adherence rates between treatment groups, assuming 2-sided hypothesis testing and an alpha level of 0.05.

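### The ±0.3 SD precision claimed for n=25 per group carries no confidence level; at the conventional 95% the half-width of a group mean is about ±0.4 SD

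*Combined protocol and SAP*

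**What the plan says.** The sample-size paragraph of Section 12.0 gives three reasons for 25 patients per group. The main one is feasibility: the numbers were "selected primarily to ensure that we can assess feasibility of providing this intervention". The second is precision: "Having n=25 patients in each group will also allow us to estimate group-specific outcomes with relatively strong precision". In brackets this is put at ± "0.3 standard deviations for continuous outcomes" and ± "10%-20% percentage points for proportions". The third is power for a between-group difference in medication adherence, "assuming 2-sided hypothesis testing and an alpha level of 0.05".

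The precision sentence has no confidence level, and none is given elsewhere in the document. It names no interval method, no range of proportions, no within-patient correlation and no allowance for dropout.

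Earlier in the same section the plan says "Analyses will be primarily descriptive in nature" and "Means, standard deviations, medians, inter-quartile ranges, and proportions will be reported on each outcome of interest, as appropriate", with results given at baseline and at 3, 6 and 12 months. On the value of the results it says "All this information will be vital for designing a future, definitive randomized controlled trial".

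**The concern.** A half-width means nothing until its confidence level is known. With 25 patients it runs from 0.26 SD at 80% confidence to 0.39 SD at 95% (normal quantiles), so the reader cannot tell what the plan promises. Most readers will assume 95%, and on that assumption the figure is too favourable.

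The stakes are modest but not nil. The pilot is mainly descriptive, so precision is a large part of what it delivers, and the plan describes that precision as strong. A later trial team that took ±0.3 SD as a 95% margin would think the pilot estimates firmer than they are.

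**Working it through.** **Inputs.** n = 25 per group, stated precision ±0.3 SD, stated range ±10 to 20 points for proportions, and two-sided alpha 0.05 (attached to the power sentence only), all from Section 12.0. Precision is in SD units, so no outcome SD is needed. All 25 patients are assumed to contribute at the time point.

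**Formulas.** For a group mean, half-width in SD units = critical value / √25 = critical value / 5. For a proportion (normal approximation), half-width = z × √(p(1−p)/25).

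**Trying to reproduce ±0.3 SD.** Exactly 0.3 needs a critical value of 0.3 × 5 = 1.5. That is two-sided confidence of 86.6% (normal) or 85.3% (t, 24 df), neither a usual level.

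**Half-widths by level.**

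| Confidence | Mean, normal (SD) | Mean, t (SD) | Proportion, p=0.1 (points) | Proportion, p=0.5 (points) |
|---|---|---|---|---|
| 86.6% | 0.300 | 0.311 | 9.0 | 15.0 |
| 90% | 1.645/5 = 0.329 | 1.711/5 = 0.342 | 9.9 | 16.4 |
| 95% | 1.960/5 = 0.392 | 2.064/5 = 0.413 | 11.8 | 19.6 |

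**Size of the gap at 95%.** 0.392/0.3 = 1.31 and 0.413/0.3 = 1.38, so 31% to 38% wider than stated.

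**Does rounding explain it?** Not at 95%, where both values round to 0.4. A half-width rounds to 0.3 only if it is below 0.35, that is, up to 92.0% confidence (normal) or 90.7% (t). At 95% that would take 32 (normal) or 34 (t) patients per group; a half-width of 0.3 or less would take 43 or 46. At 90%, 0.329 and 0.342 do round to 0.3.

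**Do the two stated figures fit each other?** At p = 0.5 the SD of a binary outcome is 0.5, so under the normal approximation the widest proportion half-width is half the SD-unit half-width, whatever the level. Then ±0.3 SD gives 0.3 × 0.5 = 15 points at most, and ±20 points pairs with 0.20/0.5 = 0.40 SD. If 0.3 is a rounded value, just below 0.35 SD still gives less than 17.5 points.

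**What the proportion range says about the level.** The upper end, 20, is closer to 95% (19.6) than to 90% (16.4). The lower end, 10, is closer to 90% (9.9 at p = 0.1) than to 95% (11.8). However, p = 0.1 is my choice; at 95%, p = 0.07 gives 10.0. Exact (Clopper-Pearson) average half-widths are 12.5 points (2/25) and 20.4 (12/25) at 95%, and 10.8 and 17.7 at 90%. The range does not settle the level.

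**Other estimands at 95%.**
- Mean of four visits with common correlation ρ: multiply by √((1+3ρ)/4). This reaches 0.3 only if ρ is at most 0.45 (normal) or 0.37 (t).
- Mean change in baseline-SD units: multiply by √(2(1−ρ)). This reaches 0.3 only if ρ is at least 0.71 (normal) or 0.74 (t).
- Both groups pooled (n = 50): 0.277 (normal) or 0.284 (t), but the claim is for each group.

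The document gives no correlation.

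**The case against.** The strongest reply is that nothing has been shown to be miscalculated. The alpha of 0.05 qualifies a different sentence, about power for a group comparison, and need not carry over to the precision statement. If 90% was meant, 0.33 to 0.34 SD is 0.3 at the one decimal the plan uses, and the lower end for proportions fits 90% better. The section also plans mixed models with repeated measures, so a more precise estimand is not ruled out. Finally, the sample size rests on feasibility, and the next trial would draw on the observed means and SDs, not on this planning remark.

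Much of this stands. The 95% level is an inference, 90% with rounding is a possible reading, and the practical effect is small. A reader might infer that ±0.3 SD is a proven arithmetic error, or that 25 per group is too few. The document supports neither: the figure cannot be called wrong at every level when no level is given, and the precision claim is not the main basis for the sample size.

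Two things survive the reply. Under the normal approximation no single level gives both ±0.3 SD and ±20 points. And the repeated-measures route needs correlations that the plan never states, while its descriptive summaries are set out visit by visit.

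**Conclusion.** The point holds as a low-severity correction. The missing confidence level is certain. At 95%, the precision for a group mean at one time point is ±0.39 to ±0.41 SD, about a third wider than the stated ±0.3 SD. At 90% it is 0.33 to 0.34 SD, which matches only after rounding; taken strictly, ±0.3 SD holds only up to about 85% to 87% confidence.

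The conclusion assumes a single-visit group mean and complete data on 25 patients, and the one-third figure also assumes that 95% was intended. Missing data would widen the intervals at any level.

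**What to change.** Restate the sentence with its confidence level and figures from one method. If 95% was meant, for example: *With 25 patients per group, 95% confidence half-widths are about ±0.4 SD (0.41 using the t distribution) for continuous outcomes and about ±12 to 20 percentage points for proportions between 10% and 90%.* If 90% was meant, say so and give about ±0.34 SD and ±10 to 16 points. If a change score or an average over visits was meant, name it and state the assumed within-patient correlation.

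The cost is one sentence, with no change to sample size, analysis or conduct.

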6.0 Number of Subjects

Sample size of n=25 patients in the Patient Navigation Group and n=25 patients in the Usual Care Group.

Patients who meet eligibility criteria and provide informed consent to participate in the LPNP will be enrolled up to the sample size goal of 25 patients. Upon completion of all study visits for the Patient Navigation Group, 25 additional patients who meet the inclusion criteria will be identified through the CCCR biorepository study to be included in the Usual Care group. Healthcare utilization and medication compliance data will be provided via a formal request (see Sections 12 & 13 below) to the CCCR and provided to study staff.

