- 9) MacArthur Scale of Subjective Social Status (MacArthur Ladder).

Post 3, 6, & 9 Month In Person or Remote Visits:

- 1) Medication Adherence Diary review,
- 2) Steps to Care Reassessment Form,
- 3) LupusPRO survey.

Post 12-Month In Person or Remote Visit:

- 1) Medication adherence diary review,
- 2) Steps to Care Reassessment Form,
- 3) LupusPRO Survey,
- 4) Perceived Stress Survey,
- 5) Social Support Survey,
- 6) Modified Picker Survey Patient-Centered Care Questionnaire,
- 7) Experiences of Discrimination (EOD) measure,
- 8) MacArthur Scale of Subjective Social Status (MacArthur Ladder).

Monthly Phone Calls post signing of informed consent:

- 1) Steps to Care Reassessment Form

The PN will contact enrolled patients to provide appointment reminders. Contacts can be via phone, text, email, or MyChart as preferred by participant. These appointments are not only standard of care rheumatology visits but also associated to the research study in question. These contacts will be completed 15 days and 2 days prior to rheumatology clinic visit.

Additionally, the PN will call the patients one week following any changes in medications for their SLE (per primary Rheumatologist or patient reported) and will ensure patient has filled in proper

information on their Medication Adherence Diary during that contact. The PN will respond to phone calls from participating patients for health and general questions, notifying the appropriate medical provider when necessary and documenting all patient-initiated calls in the EMR. The PN will assess whether the patients' basic needs are being met (i.e. are there adequate resources for food, housing, medications, etc.) and make referrals for support services as needed (to include referrals for dietary modification, smoking cessation, exercise, obesity prevention, psychiatry, and substance abuse).

For each of these in-person visits with surveys, participants will be compensated \$10 (for a total of \$50.00 over 12 months of participation). Compensation will be delivered via ClinCard. The in-person PN visits will be planned in conjunction with scheduled outpatient clinic visits.

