14.0 Withdrawal of Subjects

Subjects can withdrawal at any time during the 12-month study simply by verbally telling the PN either in person or over the phone they wish to withdraw.

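### The claim of more than 80% power for *moderate* adherence differences gives no effect size, and its stated inputs do not support it

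*Combined protocol and SAP*

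**What the plan says.** Section 6.0 sets the size: "Sample size of n=25 patients in the Patient Navigation Group and n=25 patients in the Usual Care Group". Section 12.0 explains that these numbers "were selected primarily to ensure that we can assess feasibility of providing this intervention in this high-risk population", and then adds that "our sample sizes will also provide sufficient power (>80%) to detect moderate differences in medication adherence rates between treatment groups". The test is to be two-sided at the 5% level. No difference, SD, usual-care adherence rate, within-patient correlation, weighting loss or dropout allowance accompanies the claim. It is also unclear whether an adherence rate is a per-patient quantity or the proportion of patients who adhere.

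The between-group analysis in Section 12.0 is a generalized linear mixed model with propensity score weighting, "adjusting for relevant baseline covariates (e.g. age, SLEDAI) and accounting for repeated measures within patients over time". The covariates are examples only, so baseline adherence is neither specified nor excluded. The same section plans adherence summaries at baseline and at 3, 6 and 12 months. Section 10.0 adds a month 9 diary review for the navigator group ("Post 3, 6, & 9 Month In Person or Remote Visits"). For usual care it describes no study visits: adherence comes from pharmacy records, with no measurement times given. Section 14.0 states that "Subjects can withdrawal at any time during the 12-month study".

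**The concern.** A power figure means something only together with the difference it refers to. Here that difference is a single adjective, so nobody can check the figure or learn what the comparison can detect. Medication adherence is the primary outcome. A reader told that power exceeds 80% could take an inconclusive between-group result as evidence against a moderate effect. That inference would be safe only if *moderate* meant a difference the study can in fact detect, and the simplest calculation on the stated inputs puts that difference high.

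**Working it through.** **Inputs from the documents.** n = 25 per group (Section 6.0); two-sided alpha 0.05 and power above 80% (Section 12.0). Everything else below is an assumption and is marked as such.

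**1. The plan's own figure.** It cannot be reproduced, because the effect size is missing. The calculation can only be run in reverse: what difference gives 80% power?

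**2. Continuous adherence, one time point, unadjusted t test.** The noncentrality is d × √(n/2) = d × √12.5 = 3.536 d, with 48 degrees of freedom and critical value 2.011.

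| Difference d (SD) | Noncentrality | Power |
|---|---|---|
| 0.5 | 1.768 | 41% |
| 0.6 | 2.121 | 55% |
| 0.7 | 2.475 | 68% |
| 0.8 | 2.828 | 79% |

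Solving for 80% gives d = 0.81.

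**3. Binary adherence, one time point, usual-care rate assumed to be 50%.** Power = Φ[(|p2 − p1| − 1.96 s0)/s1], with s0 = √(2p̄(1 − p̄)/25) and s1 = √([p1(1 − p1) + p2(1 − p2)]/25). For 50% v 86.1%, s0 = 0.1319 and s1 = 0.1216, so (0.361 − 0.2585)/0.1216 = 0.843 and power is 80%. The detectable difference is about 36 points, or 38.9 points by Fisher's exact test. At other assumed usual-care rates (30%, 40%, 60%) it is 38.7, 38.1 and 32.8 points, or 40.8, 40.5 and 34.5 by Fisher. A 20-point difference from 50% has about 30% power (23% by Fisher).

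**4. Repeated measures, before any losses.** Assume a continuous outcome, the same effect at every time and equal correlation ρ between measurements. The variance of a patient's mean over m follow-up measurements is then multiplied by (1 + (m − 1)ρ)/m, less ρ² if baseline adherence is a covariate. Example: m = 3, ρ = 0.5, no baseline adherence gives 2/3; noncentrality 1.768/√0.667 = 2.165; power 56%. For ρ = 0.3 / 0.5 / 0.7:

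| d (SD) | m | Without baseline adherence | With baseline adherence |
|---|---|---|---|
| 0.5 | 3 | 66 / 56 / 49% | 74 / 77 / 88% |
| 0.5 | 4 | 71 / 59 / 50% | 80 / 81 / 90% |
| 0.7 | 3 | 91 / 84 / 77% | 95 / 96 / 99% |
| 0.7 | 4 | 94 / 87 / 79% | 97 / 98 / above 99% |

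Simulation gives 79%, 80% and 89% for the case d = 0.5, m = 4 with baseline adherence, so at the two lower correlations that case lies on the 80% line. Without baseline adherence, 80% at 0.5 SD needs ρ of at most 0.07 (m = 3) or 0.18 (m = 4).

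**5. The number of measurements is itself an assumption.** The month 9 visit belongs to the navigator group, and the 3, 6 and 12 month times are for descriptive reporting. Usual-care pharmacy adherence could be a single 12-month value (m = 1, the 41% of step 2 at 0.5 SD) or something more frequent. With an assumed m = 12, ρ = 0.3 and no baseline adherence, the factor is (1 + 3.3)/12 = 0.358 and power at 0.5 SD is about 83%.

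**6. Losses.** An assumed design effect of 1.5 from weighting reduces 25 per group to an effective 25/1.5 = 16.7. At 0.5 SD with baseline adherence and three or four measurements, power then falls to about 56% to 75%.

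**The case against.** The strongest reply is that the t test is not the planned analysis. That stands. A repeated-measures model with baseline adherence as a covariate can exceed 80% at 0.5 SD if losses are small, and at 0.7 SD most of the cases in step 4 do so. Nothing in the plan equates *moderate* with 0.5 SD either. A reader might infer from step 2 that the study's real power is 41% and that the claim is false. The documents do not support that: they plan a different and generally more efficient model, and leave open the inputs that would settle its power.

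A reader might also condense calculations like those in step 4, with design effects up to 1.5, into one range of detectable differences, about 0.43 to 0.90 SD, and attach it to the planned model. That is not supported either. Such a range reflects chosen correlations, design effects and three or four measurements. It is not even an outer bound: 0.769 SD for an assumed 20 v 25 after withdrawals (three measurements, ρ = 0.7, no baseline adherence), multiplied by √1.5 for weighting, is about 0.94 SD.

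The combined dataset with the collaborating site does not rescue the figure. No sample size is given for that site, and the power sentence rests on 25 per group.

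Finally, the analyses are mainly descriptive and the size was chosen chiefly for feasibility. That stands too, and limits the weight of the point. It does not supply the missing effect size.

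**Conclusion.** The claim of more than 80% power is unsupported as written. *Moderate* is undefined, and the stated inputs in a simple comparison give 80% power only at about 0.81 SD (about 36 to 39 points with an assumed 50% usual-care rate). They give about 41% at 0.5 SD, where 0.5 SD is an assumed reading of the word. Whether the planned weighted mixed model exceeds 80% cannot be determined from the documents. It can under favourable assumptions and fails under others, and no single range of detectable differences can be assigned to it. Severity is minor: this is a gap in justification within a feasibility pilot and does not undermine its design.

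**What to change.** Either of two changes to the sample-size text in Section 12.0 would do.

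- Replace the power sentence with the detectable difference, for example: *As an unadjusted reference at a single time point, 25 patients per group and a two-sided 5% test give 80% power for a difference of about 0.81 SD (about 36 to 39 percentage points if adherence is binary and the usual-care rate is assumed to be 50%). This is before any gain from repeated measures and covariate adjustment, and before any loss from propensity weighting and withdrawals.*
- Or keep the 80% figure, together with the inputs that produce it under the planned model: numeric effect size and scale, within-patient correlation, number of adherence measurements available in both groups, whether baseline adherence is a covariate, and the assumed losses from weighting and withdrawal.

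The second option matches the planned analysis more closely but requires the team to commit to those assumptions. The cost is one or two sentences, with no change to sample size, procedures or model. The downside is a less favourable headline figure, or assumptions that become open to challenge.

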13.0 Provisions to Monitor the Data to Ensure the Safety of Subjects

The investigator and other study personnel will keep confidential any information related to this study, all data and records generated during conducting the study, and will not use the information, data, or records for any purpose other than conducting the study. These restrictions do not apply to: (1) information that becomes publicly available through no fault of the investigator or site personnel; (2) information that is necessary to disclose in confidence to an IRB solely for the evaluation of the study; (3) information that is necessary to disclose in order to provide appropriate medical care to a patient; or (4) study results that may be published in an aggregate fashion.

All data will be stored on MUSC Network Storage with survey results entered into a secure MUSC REDCap database, only accessible by personnel approved on this study application with MUSC login credentials. The data from the two institutions (MUSC and UAB) will be maintained separately, with data entry and editing performed only by IRB-approved personnel specific to each site.

Patients will be assigned an identification number. Personal identifiers will not be accessible to individuals beyond the investigative site. Confidentiality will be maintained by the use of codes for identifiers. All study related documents (physical paper documents, if needed) and materials will be

kept in secured locked file cabinets in a locked office space of the Division of Rheumatology with limited access by non-study personnel.

14.0 Withdrawal of Subjects

Subjects can withdrawal at any time during the 12-month study simply by verbally telling the PN either in person or over the phone they wish to withdraw.

